PROJECT TITLE:

COVID-19 Testing in Underserved and Vulnerable Populations Receiving Care in San Diego Community Health Centers

NCT: 05315908

Date: 4/6/2021

RESEARCH DESIGN AND METHODS

Community Partner Program and Study Setting

The proposed testing project will leverage existing community health center (CHC)-academic partnerships under the NCI-funded Accelerating Colorectal Cancer Screening and Follow-up through Implementation Science (ACCSIS) Cancer Moonshot grant (UG3CA233314), whose goal is to improve colorectal cancer (CRC) screening among medically underserved populations. This partnership include UCSD and Health Center Partners (HCP) and its subsidiary, Health Quality Partners (HQP). HCP/HQP is a non-profit consortium of 16 CHCs that provide primary care to meet the health needs of communities in Southern California. HCP members collectively operate over 160 clinic sites that include urban, rural, agricultural worker, and US-Mexico border populations, and serve over **858,000 vulnerable patients with 3.6 million patient visits** each year. CHCs have been at the front lines of health care in the nation's poorest neighborhoods for decades. High risk asymptomatic patients served by these centers are not getting proper testing, include essential workers, and could contribute to further spread of the virus. For these reasons, HCP/HQP, our community partner, approached the academic partner with interest in submitting this application.

[figure not shown]
Participating CHCs. CHC participation involved a process of several presentations that outlined the concept and deliverables and elicited feedback from the medical directors, providers, and staff. Following these, three CHCs indicated interest and capacity to participate: Neighborhood Healthcare (Neighborhood), Vista Community Clinic (Vista), and La Maestra CHC (La Maestra).

Study Methodology

AIM 1: Compare the effectiveness of automated call vs text messaging for uptake of COVID-19 testing among asymptomatic adult patients with select medical conditions and those 65 years of age and older receiving care at participating CHCs.

We will include asymptomatic CHC patients with at least one clinic visit in the last year, age 21 years and over, with medical conditions deemed by the Centers for Disease Control and Prevention to increase risk for severe COVID-19 illness⁸, including heart failure, coronary artery disease, cancer, chronic kidney diseases, COPD, obesity, sickle cell disease and type 2 diabetes mellitus, and those 65 years of age and older. We estimate that ~40% of CHC patients will have at least one medical condition (~35,000 eligible). We will use our team's extensive experience with existing protocols from our ongoing ACCSIS colorectal screening mailed stool testing intervention as models for the COVID-19 testing project, which have been culturally adapted and tailored for CHC patients.^{12,13} CHC staff will mail an introductory letter to eligible individuals describing the importance of COVID-19 testing, inviting them to receive a test, offering opt out instructions, and noting that follow-up contact (phone call, SMS text message) will take place if they do not opt out. Patients who do not opt out, and those whose mail is not returned, will be randomized one week after the introductory letter is mailed.

Randomization. CHC patients will be randomized to one of two arms (see **Figure 2**). Stratification by CHC will not be done due to large sample size.

- 1) Patients in the Automated call condition will receive up to two automated phone calls in English or Spanish depending the patients' language indicated in their electronic health record (EHR), between the hours of 10:00am and 9:00pm Monday through Friday.
- 2) Patients in the text (SMS) condition will receive up to two text messages in English or Spanish. The automated call and text messaging will instruct patients to call a staff member at the health center's COVID-19 testing center to schedule COVID-19 test.

COVID-19 Testing and Capacity

Randomized patients who are reached will be provided with information on the study and invited to make a clinic appointment for testing. We will use a rapid, high-throughput SARS-CoV-2 qRT-PCR-based diagnostic assay certified for clinical use under FDA Emergency Use Authorization (EUA) that was developed at the UCSD Biochemical Genetics and Metabolomics Laboratory (BCG), a CLIA/CAP certified laboratory. Our process requires 24-48 hours from receipt of samples to reporting of results. Anterior nares swabs will be collected by the patient and placed into automation-ready collection tubes containing PrimeStore Molecular Transport medium, which inactivates pathogens (including the SARS-CoV-2 virus) and stabilizes RNA. We will use Redox middleware to integrate testing laboratory information system (LIS) with the CHC EHR systems. Redox is also set up for required reporting to local, state, and federal agencies through the California Reportable Disease Information Exchange - Electronic Lab Reporting (CalREDIE ELR). Per state guidelines, the testing laboratory is required to report positive and negative test results to the County health department using a standard morbidity report. Positive cases are followed by the County for contact tracing.

Two novel features embedded in this study.

- 1) In an opportunistic way, we will offer the flu vaccine to patients as part of standard of care at the time of COVID testing. Given recent reports of possible reluctance by individuals to re-engage in health care, including flu vaccination,¹⁴ and with flu season underway, we must prepare for the challenges of its usual dangers combined with novel impacts of COVID-19. This provides an ideal educational opportunity to promote COVID-19 vaccination through positive messaging.
- 2) We will also assess feasibility and acceptability of COVID-19 testing of study participants' adult household members who are essential workers. When a CHC patient contacts a clinic to make a testing appointment, clinic staff will ask him/her if he/she lives with an essential worker,

as defined by the state of California.¹⁵ If essential workers reside in the home, the participant will be asked if they are willing to refer the household member for COVID-19 testing.

Data Collection, Harmonization and Reporting.

Data collection via EHR and patient surveys will include the PhenX Toolkit core elements including age, sex, race and ethnicity, address, access to health services, income, employment status, education, English proficiency, food insecurity, gender identity, sexual orientation, health insurance, health literacy, and occupation. We will also include household size, foreign-born status, and job type, given that these factors contribute to higher infection rates in Latinx communities,⁶ as well as trust in healthcare¹⁶ and discrimination, which are important for our Latinx population. We will work with our advisory board members, community collaborators, stakeholders, the health center leaderships to select additional data elements from the PhenX Specialty collections.

Primary Study Endpoints.

For efficacy assessment, our primary study outcome will be the proportion of patients who undergo testing within one month of initial contact (automated call and text messaging). We will also assess the proportion of patients who undergo testing by the end of the study period (to consider individuals who could not come to the clinic within one month). Secondary endpoints of interest include: number (%) tested (total and by clinic), number (%) infected (total and by clinic). We will also assess the timeliness of testing (from time of contact to testing).

Secondary Study Endpoints.

For flu vaccination, our endpoint will be number vaccinated. For essential worker referral to COVID-19 testing, we will measure *Feasibility* by: a) ascertainment of essential worker status; and b) willingness to offer testing invitation to eligible household member(s). *Acceptability* will be assessed by: a) the proportion of study participants with eligible household members who refer household member(s); and b) the number of household members referred for testing.

Sample Size and Study Power.

Number of study participants was driven by budget, capacity to deliver as many tests as possible, and number of eligible patients at the participating CHCs. Since routine testing of asymptomatic patients is not taking place at the CHCs, we expect that most eligible patients (~35,000) will not be tested. Based on our prior work, we expect ~5% undeliverable calls due to wrong numbers. The exact number of participants randomized in each arm to derive at **9,000 (4,500 per arm)** will be determined by testing uptake rates and an estimated 10% drop off rate due to no shows for testing, with assumption of missing completely at random. To our knowledge, there are no existing data to inform effect size. We thus estimated power for a series of proportion of testing completion between two arms Our study has >80% power with a two-sided alpha=0.05 to detect proportion of testing completion as high as 0.5 in the automated call and 0.7 in the text messaging , and as low as 0.3 and 0.5, respectively, in each corresponding arm.

Statistical Analysis.

Baseline sociodemographic and other clinical characteristics will be assessed for imbalance among the 2 study arms using t-test or chi-square tests for categorical variables. In our primary analysis, we will compare proportion of patients who undergo COVID-10 testing within one month following initiation/randomization between the two study arms using an intention-to-treat approach. For our primary analysis, will use Fisher's exact test for an overall comparison of testing completion between two groups using a P<.05 as statistical significant threshold. We will estimate risk ratios and 95% confidence intervals as the measure of association between

intervention groups and testing completion. We will also explore testing rates between groups stratified by social determinants of health factors and other key factors using a likelihood ratio test, recognizing that these analyses will be better suited for the total consortium.

AIM 2: Gather patient, provider, CHC leadership, and community stakeholder insights to establish best practices for future scale-up of COVID-19 testing sustainability and vaccination.

We will use a mixed-methods approach to evaluate our COVID-19 testing strategies, materials and outcomes (acceptability, feasibility, appropriateness, sustainability). We will gather information on implementation and sustainability facilitators and barriers from individuals receiving/declining testing. Using structured interviews and a coded directed content analysis approach to analyze transcripts, we will collect comparable information for feasibility, acceptability, appropriateness, and sustainability for select providers (1 per clinic), chief medical officers in 3 participating CHCs, and 3 key community stakeholders. Measures include survey items guided by the Practical, Robust Implementation and Sustainability Model (PRISM) and (Reach Effectiveness, Adoption, Implementation and Maintenance) RE-AIM framework, and include the Feasibility of Intervention Measure (FIM), Acceptability of Intervention Measure (AIM), and Intervention Appropriateness Measure (IAM).

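### Optional small precision gain: the valid unadjusted primary analysis leaves out health center (CHC), which is known for every patient before randomisation

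*Combined protocol and SAP*

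**What the plan says.** All references are to the combined protocol and SAP.

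- **Statistical Analysis:** the primary comparison is intention-to-treat and "will use Fisher's exact test for an overall comparison of testing completion between two groups", at P<.05. On the effect measure: "We will estimate risk ratios and 95% confidence intervals as the measure of association between" arm and testing completion. No covariate is named for the test or for the risk ratio.
- **Randomization:** patients are allocated individually to automated call or text message. "Stratification by CHC will not be done due to large sample size".
- **Participating CHCs, Study Methodology and Randomization:** three CHCs take part. Eligible patients come from the CHCs' own patient lists, CHC staff mail the introductory letter, and randomisation follows one week later. CHC is therefore known for every patient at allocation. Age enters through eligibility, and the EHR language sets the language of the calls.
- **Primary Study Endpoints and Statistical Analysis:** the number and percentage tested are reported by clinic. Rates between arms are also explored "stratified by social determinants of health factors and other key factors using a likelihood ratio test". Neither of these adjusts the primary result.
- **Sample Size and Study Power:** the target is 9,000 (4,500 per arm), power is stated as above 80% for 0.3 vs 0.5 and for 0.5 vs 0.7, and the section says "there are no existing data to inform effect size".

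**The concern.** If centers differ in how many of their patients come for testing, part of the outcome variance reflects which center a patient attends. An unadjusted comparison carries that part in its standard error. A comparison made within centers removes it, using a variable that is already held.

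The reason given for not stratifying allocation is the large sample. A large sample makes chance imbalance between arms small, but it does not take between-center variation out of the standard error. The proportional narrowing from adjustment is the same at any sample size.

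Only precision is at stake. It would count only if the true difference between call and text is a few points or less. The plan does not exclude this: it has no data on effect size, and both arms get up to two contacts carrying the same instruction to call the testing center.

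**Working it through.** **Plan's own figure.** At 4,500 per arm, for 0.3 vs 0.5, SE = sqrt((0.3×0.7 + 0.5×0.5)/4,500) = 0.01011 and z = 0.20/0.01011 = 19.8. The pair 0.5 vs 0.7 gives the same z. Power is above 99.9% in both, so the stated figure of over 80% holds as a lower bound and adjustment has nothing to add there.

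**Inputs.** Two-sided alpha of 0.05, 4,500 per arm and three centers come from the documents. Uptake by center and equal center sizes are assumptions, because the documents give neither.

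**Formulas**, with p_i the uptake in center i and p̄ the mean:

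- Share of variance due to center = mean((p_i − p̄)²) / (p̄(1 − p̄))
- CI narrowing = 1 − sqrt(1 − share)
- Unadjusted SE = sqrt(2p̄(1 − p̄)/n); adjusted SE = unadjusted SE × sqrt(1 − share)
- Power for difference d ≈ Φ(d/SE − 1.96)

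**Worked case, 30/40/50%.** p̄ = 0.40. The between-center variance is (0.01 + 0 + 0.01)/3 = 0.00667 and the total is 0.24, so the share is 0.0278. Narrowing = 1 − sqrt(0.9722) = 1.4%. The SE goes from 0.01033 to 0.01018. For d = 0.02, d/SE goes from 1.936 to 1.964 and power from 49.1% to 50.2%.

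**Results at 4,500 per arm:**

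| Assumed uptake | Share | CI narrowing | 95% CI half-width (points) | Power, 2 points | Power, 1 point |
|---|---|---|---|---|---|
| 3/5/7% | 0.0056 | 0.28% | 0.901 to 0.898 | 99.2% to 99.2% | 58.6% to 58.8% |
| 40/45/50% | 0.0067 | 0.34% | 2.056 to 2.049 | 47.9% to 48.1% | 15.9% to 16.0% |
| 30/40/50% | 0.0278 | 1.40% | 2.024 to 1.996 | 49.1% to 50.2% | 16.2% to 16.6% |

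**Number randomised.** The size of each arm "will be determined by testing uptake rates and an estimated 10% drop off rate due to no shows for testing", so 9,000 can be read as patients randomised or as patients tested. The upper bound is 35,000/2 = 17,500 per arm, since patients who opt out are not randomised. At that size 2-point power goes from >99.9% to >99.9%, 96.4% to 96.5% and 96.8% to 97.2%. The relative narrowing does not change.

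**Simulation check of the Mantel-Haenszel risk ratio** (3,000 trials per scenario, 9,000 patients, simple randomisation, three equal centers). With no arm effect, the SE of the log risk ratio fell by 0.27%, 0.33% and 1.39%. Unadjusted and adjusted rejection rates were 5.0/4.9%, 5.0/4.8% and 4.8/4.7%. The simulation error on these is about sqrt(0.05×0.95/3,000) = 0.4 points, so both hold their level. With a 2-point difference, power was 99.1/99.2%, 47.6/48.0% and 49.6/50.7%, in line with the table.

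**The case against.** The strongest reply is that nothing here is wrong. An unadjusted test in an individually randomised trial with no stratified allocation is a legitimate choice, and there is no stratification factor to carry into the model. The authors gave a reason for leaving CHC out of allocation, report testing by clinic, and kept covariate work exploratory. Under modest assumptions the half-width moves by at most 0.03 points. The unsettled meaning of 9,000 matters far more: going from 4,500 to 17,500 per arm moves the half-width from 2.024 to 1.026 points in the 30/40/50% case, about 35 times the effect of adjustment (0.998/0.028). An adjusted analysis with open choices of method and covariates would also loosen a primary test that now has none.

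Most of this stands. It limits the point to an option and requires that any change name one method and one covariate set. It does not remove the point: neither the sample size, nor the by-clinic reporting, nor the exploratory analyses take between-center variation out of the primary standard error.

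A reader might infer more, and the documents do not support it:

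- **That the Fisher test is invalid, or that unstratified allocation biases it.** Randomisation protects the unadjusted comparison, and simulated rejection under no effect stays near 5%.
- **That the gain is material.** A spread such as 30/50/70% would narrow the CI by 5.5%, but nothing in the documents points to so wide a spread.
- **That age and language add a known further gain.** Both are available before randomisation, but the documents give nothing from which to size their effect.

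**Conclusion.** The planned primary analysis is valid. Adjusting for CHC is an optional improvement, worth about 0.3% to 1.4% of CI width in the modest scenarios and at most about 1.1 points of power for a 2-point difference at 4,500 per arm. At low uptake the gain is negligible, and at the plan's 20-point differences it is nil. These sizes rest on assumed uptake by center and equal center sizes. If the centers turn out alike there is essentially nothing to gain. The case for adopting it is that it costs very little, and the sponsor could reasonably decline.

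**What to change.** Before outcomes by arm are seen, prespecify one primary intention-to-treat analysis:

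- The CHC-stratified Mantel-Haenszel risk ratio with its 95% CI, and the matching Cochran-Mantel-Haenszel p-value as the single test at P<.05.
- Fisher's exact test and the crude risk ratio, reported as the unadjusted check.
- Adjustment for age and EHR language, if wanted, as a sensitivity analysis only.

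Allocation does not change and no new data are needed. The cost is SAP wording and a few lines of analysis code. The one trade-off is that the primary p-value no longer comes from an exact test, which is immaterial with thousands of patients per arm.
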